11.7.3 Populations for Analyses

The following populations for analyses are defined in [Table 21](#).

Table 21 **Populations for Analysis**

Population/Analysis set	Description
Safety	All patients who received at least one dose of AZD0466
Intention-to-treat	All patients who received at least one dose of AZD0466
Evaluable for Response	All patients who have received at least 3 doses of AZD0466 at the target dose level in Cycle 1
DLT-evaluable	Patients enrolled in the dose-escalation that have received at least 3 doses of AZD0466 at the target dose level (75% of target doses from Day 8 to Day 29 in Cycle 1) and have completed the safety follow-up through the DLT evaluation period Or Have experienced a DLT
Pharmacokinetics	Dosed patients with at least one reportable plasma concentrations and no important AEs or protocol deviations that may impact PK

AE, adverse event; DLT, dose-limiting toxicity; PK, pharmacokinetics.

11.7.4 Statistical Analyses

The SAP will include a more technical and detailed description of the statistical analyses described in this section. This section is a summary of the planned statistical analyses of the most important endpoints including primary and key secondary endpoints specific to this module.

11.7.5 General Considerations

For the dose escalation, Part A, a final analysis will be performed when the MTD has been determined and the last patient to be recruited (including any backfill patients) has had the opportunity to complete 2 cycles of treatment, or has discontinued or withdrawn from treatment. Response and survival data will continue to be collected for ongoing patients until this milestone is reached for the final patient.

For Part B, an IA will be performed when the twelfth patient has had the opportunity to complete one cycle of treatment and is response evaluable as per [Table 21](#). This analysis will include evaluation of clinical response and AEs leading to discontinuation. Provided recruitment is not stopped due to futility or safety concerns, a second IA will be performed once all patients recruited have had the opportunity to complete one cycle of treatment, with efficacy analyses based on the ITT population. The final analysis of the expansion cohorts will be undertaken when either the last patient from all expansion cohorts has had the opportunity to complete 6 months of treatment, or all patients have withdrawn from the study or died. Thereafter, patients who are still on study treatment may remain on treatment and individual patients will continue to be assessed for safety as specified in the protocol.

11.7.6 Efficacy

Part B: Calculation or Derivation of Efficacy Variables

Patients will be assigned a response of CR, CR_i, MLFS, PR, CR_c, CR_m, Relapse or Failure for according to the criteria described in [Appendix J](#) for AML or CR, CR_i, Failure, or Relapse according to the criteria in [Appendix K](#) for ALL. This is regardless of whether visits were scheduled or unscheduled and also regardless of whether a patient discontinues study intervention or receives another anticancer therapy.

The disease response endpoints (CR+CR_i, time to response [TTR], and DoR) will then be derived from the bone marrow biopsy dates and overall visit responses.

Complete response rate is defined as the proportion of patients with a best response of CR or CR_i. Any treated patient who has not satisfied the criteria for CR or CR_i will be treated as a non-responder for this analysis.

Time to response is defined as the time from date of first dose until the date of first documented CR or CR_i. The analysis will include all dosed patients who have a complete response. Patients who go off treatment without a clinical response, receive a subsequent therapy, and then respond will not be included.

Duration of response will be defined as the time from the date of first documented response (CR or CR_i) until date of documented progression, relapse or failure according [Appendix J](#) for AML and [Appendix K](#) for ALL or death due to any cause. Patients who are not known to have reached one of these endpoints at the time of data cut-off (DCO) will be censored at the last overall response assessment on or before the start of subsequent therapy.

Overall survival is defined as time from date of first dose until the date of death due to any cause. For patients who are alive at the time of DCO, OS will be censored on the last date when patients were known to be alive. Note: Survival calls will be made following the date of DCO for the analysis (these contacts should generally occur within 7 days of the DCO). If patients are confirmed to be alive or if the death date is after the DCO date, then these patients will be censored at the date of DCO.

Analysis Methods

The primary efficacy variable will be the Complete Response Rate (CR+CR_i). Complete response rate will be estimated with exact 95% confidence intervals based on the exact binomial distribution. Lower one-sided 80% and upper one-sided 90% limits will also be calculated.

For AML patients, other outcomes such as overall response rate (ORR) (best response of CR+CR_i+PR) and Leukaemia Response Rate (best response CR+CR_i+PR+MLFS) will be

summarised with two-sided 95% confidence intervals based on the exact binomial distribution.

Changes in platelets, blasts and neutrophils will be summarised over time.

All response outcomes will be listed.

Time to response, DoR, and OS will be analysed using the Kaplan-Meier method. Quartiles, including the median, will be calculated along with 95% confidence intervals as well as rates at 3, 6, 9, and 12 months post first dose.

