
 To estimate the preliminary antitumor activity of AZD0466 by assessment of DoR in patients with advanced haematological malignancies. 	
 DoR will be defined as the time from the date of first documented response (CR+CR_i) until date of documented progression, relapse or failure per Appendix J and Appendix K or death due to any cause. The analysis will include all dosed patients as intended who have a confirmed response (CR or CR_i), regardless of whether the patient withdraws from study treatment or receives another anticancer therapy. The measure of interest are the percentiles of DoR.

Table 13 Secondary Objectives - Module 1

Objectives	Estimand description
Overall Survival (OS)	

 To estimate the preliminary antitumor activity of AZD0466 by assessment of OS in patients with advanced haematological malignancies. 	
 OS is defined as time from date of first dose until the date of death due to any cause. The comparison will include all dosed patients as intended, regardless of whether the patient withdraws from therapy or receives another anticancer therapy. The measures of interest are the median OS and landmarks at 6 and 12 months of OS.

ALL, acute lymphocytic leukaemia; AML, acute myeloblastic leukaemia; CR, complete remission; CR_i, incomplete haematological response; DoR, duration of response; OS, overall survival; TTR, time to response

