13 CHANGES IN THE CONDUCT OF THE STUDY OR PLANNED ANALYSIS

As per the protocol, Section 11.7.6, analysis of efficacy data from Module 1 was to include data from Part B of Module 1. As Module 1 Part B was not initiated, and if data allow, the analyses described in Section 11.7.6 of the protocol will be applied to Module 1 Part A data.

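### Duration of response back-dates censoring to before new therapy only for responders who stay event-free, so censoring depends on outcome and does not fit the stated estimand

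*Protocol*

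**What the plan says.** Protocol 11.7.6 runs DoR from the first documented CR or CRi "until date of documented progression, relapse or failure according" to the response appendices, or to death from any cause. It has no clause that removes events after a new therapy. The same section assigns response, relapse and failure categories "regardless of whether a patient discontinues study intervention or receives another anticancer therapy".

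Censoring applies only to patients with no known endpoint at data cut-off. They "will be censored at the last overall response assessment on or before the start of subsequent therapy". DoR is then analysed by Kaplan-Meier together with time to response and overall survival, with quartiles "as well as rates at 3, 6, 9, and 12 months post first dose".

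Protocol Table 13, in its estimand column, describes the DoR analysis as covering responders "regardless of whether the patient withdraws from study treatment or receives another anticancer therapy". SAP 6.2 repeats this.

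SAP v2.0 was written after the study was terminated and without Part B. It has no DoR analysis section, but SAP 13 says that, if the data permit, "the analyses described in Section 11.7.6 of the protocol will be applied to Module 1 Part A data".

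**The concern.** Kaplan-Meier needs the censoring time to carry no information about the later outcome. Here the censoring date is chosen after looking at that outcome. Two responders may start the same new therapy on the same day. If one relapses six months later, that patient contributes the whole interval and an event. If the other stays in remission, that patient's time after the switch is discarded. Good outcomes after a switch are lost and bad ones are kept.

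The situation can arise. Protocol section 8 follows patients in CR or CRi for relapse until death, so relapses and deaths after a switch can be recorded. What is at stake is a DoR summary that is too short and does not estimate the quantity named in Table 13.

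**Working it through.** The documents give no DoR assumption, event count or switching rate, so there is no planned figure to reproduce. The check has three steps.

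**1. Direction, without assumptions.** The Kaplan-Meier estimate is S(t) = ∏(1 − dⱼ/nⱼ) over event times up to t, where dⱼ is the number of events and nⱼ the number at risk. Compare the rule in 11.7.6 with following every responder through new therapy. The events and their dates are the same, so every dⱼ is the same. Event-free switchers leave earlier, so every nⱼ is equal or smaller. Each factor is therefore equal or smaller, and the curve can only move down.

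**2. Worked example (invented data).** Ten responders, cut-off at month 12. Four switch at month 2: two relapse at month 8 and two stay event-free. Six do not switch: two relapse at month 5 and four stay event-free.

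- Follow everyone through the switch: S(9) = (1 − 2/10)(1 − 2/8) = 0.80 × 0.75 = 0.60; median not reached.
- Rule in 11.7.6: two leave at month 2, so S(9) = (1 − 2/8)(1 − 2/6) = 0.75 × 0.667 = 0.50; median 8 months.
- Censor all four at the switch: S(9) = 1 − 2/6 = 0.67; median not reached.

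**3. Size under assumed inputs.** Every input is an assumption: exponential DoR with true median 6 months, follow-up of 3 to 12 months after response, and a given share of responders assigned a switch at 1 to 3 months, independent of prognosis. A patient who relapses first never switches in remission. For a switch at 2 months, 0.5^(2/6) = 0.79 of those assigned are still in remission. Results under the rule in 11.7.6:

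| Share assigned a switch | Median DoR (months) | 6-month rate |
|---|---|---|
| none | 6.0 | 50% |
| 5% | 5.9 | 49.3% |
| 10% | 5.7 | 48.4% |
| 20% | 5.5 | 46.7% |
| 30% | 5.3 | 44.8% |
| 50% | 4.7 to 4.8 | about 40% |

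In the same simulations, both consistent rules (ignore the switch, or censor every switcher at it) return about 6.0 months and 50%. The one-sided rule alone produces the shortfall.

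A second set of assumptions used true medians of 4, 6 and 9 months, constant switching rates of 0.03 to 0.12 per month and assessments every 28 days. The shortfall in the median ran from 1 − 3.86/3.99 = 3% to 1 − 6.50/8.97 = 28%.

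**Clock for landmark rates.** The sentence in 11.7.6 dates the rates for all three time-to-event endpoints from first dose. Time to response and overall survival start there; DoR starts at first response.

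**The case against.** Four points can be made for the plan.

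*The rule may never be used.* It stands in 11.7.6 under a Part B heading, and Part B was not initiated. SAP 8.10 names only complete response and overall survival as efficacy endpoints, and SAP 8.10.2 has methods for those two alone. SAP 4.3.1 says no data cut-off applies, although the rule is tied to one. A reader might infer that a biased DoR analysis is firmly planned. The documents do not support that: SAP 13 is conditional. They do not rule it out either, because DoR remains a secondary objective in SAP 6.2 and has an analysis set in SAP Table 6.

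*Switching in remission may be rare.* Protocol 6.8 expects subsequent treatment to follow recurrence or a new cancer. After recurrence the DoR event has already happened and back-dating cannot apply. A reader might take the 30% or 50% rows as the expected bias; nothing in the documents supports those rates. With ten responders (an assumed number) the standard error of a 50% rate is about √(0.5 × 0.5/10) = 16 points even without censoring, against a shift of 50 − 48.4 = 1.6 points at 10% switching. This stands as a limit on size.

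*Table 13 might only define who is included.* The clause follows the description of patients "who have a confirmed response (CR or CR_i), regardless of whether the patient withdraws from study treatment or receives another anticancer therapy", so it could be read as an inclusion rule, with 11.7.6 supplying the censoring. In a column that describes estimands, the more natural reading is that other therapy is disregarded. Even on the narrower reading, the one-sided censoring remains.

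*The clock is a wording slip.* This is fair. It would be too strong to call the DoR rates uninterpretable: the DoR origin is clear in 11.7.6, Table 13 asks for percentiles, and SAP 8.10.2.2 gives landmark rates for overall survival only.

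**Conclusion.** Wrong as written. The downward direction follows from the text and the Kaplan-Meier formula alone, and the rule does not match the estimand in Table 13 and SAP 6.2. If the intention was to censor everyone at new therapy, 11.7.6 does not say so, and that too would conflict with Table 13.

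The size cannot be derived from the documents. Under the stated assumptions it runs from about 0.1 month off a 6-month median at 5% switching to about 1.2 to 1.3 months at 50%; the low end is more in keeping with Protocol 6.8.

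The practical consequence is limited. DoR is descriptive, no hypothesis is tested, the Part B decision rules used CR+CRi only, and the error shortens DoR rather than flattering the drug. It matters only if DoR is produced for Part A under SAP 13; in that case 11.7.6 is the only censoring rule available.

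**What to change.** - In Protocol 11.7.6, and in the SAP if DoR is reported, censor event-free responders at their last response assessment whether or not new therapy has started. This matches Table 13.
- If a sensitivity analysis that censors at new therapy is wanted, apply it to every switcher, including those who later relapse, progress or die, and label it as a different estimand.
- Date the DoR landmark rates from first response; leave first dose as the origin for time to response and overall survival.

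The cost is one censoring sentence and one clause on the clock in 11.7.6. The SAP has no DoR section to edit, so reporting DoR would need a short new paragraph there. No additional data collection is needed, because follow-up for relapse already continues until death.

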11.7.7 Safety

There are no module-specific safety analyses planned.

11.7.8 Other Analyses

11.7.8.1 Pharmacokinetics

Calculation or Derivation of Pharmacokinetic Variables

Pharmacokinetic analysis of the plasma and urine concentration data for total and released AZD4320 and its metabolites (if available and appropriate), when applicable, will be derived using non-compartmental methods in Phoenix® WinNonlin® Version 8.1 or higher (Certara) performed by Covance on behalf of the sponsor. The PK parameters are calculated/estimated according to AstraZeneca standards.

PK analysis will, where data allow, be carried out using actual elapsed times determined from the PK sampling and dosing times recorded will be used in the database. If actual elapsed times are missing, nominal times may be used. Nominal sampling times may be used for any agreed interim PK parameter calculations and PK parameters will be derived using standard non-compartmental methods.

Where data allow, the following PK parameters for total and released AZD4320 will be derived from plasma and urine concentrations:

Plasma

C_{\max}	Maximum observed plasma (peak) drug concentration
t_{\max}	Time to reach peak or maximum observed concentration or response following drug administration
λz	Terminal rate constant, estimated by log-linear least squares regression of the terminal part of the concentration-time curve
$t_{1/2\lambda z}$	Half-life associated with terminal slope (λz) of a semi-logarithmic concentration-time curve
AUC_{0-72}	Partial area under the plasma concentration-time curve from time 0 to 72 hours after the start of infusion
AUC_{last}	Area under the plasma concentration-curve from time 0 to the last quantifiable concentration
AUC_{cml}	Area under the plasma concentration-curve from time 0 on Day 1 through the first full dose on Day 8 and extrapolated through infinity.
t_{last}	Time of last observed (quantifiable) concentration
C_{trough}	Concentration prior to dosing
Dose normalised AUC_{last}^a	Area under the plasma concentration-time curve from time 0 to time of last quantifiable analyte concentration divided by the dose administered
Dose normalised AUC_{0-72}^a	Area under the plasma concentration-time curve from time 0 to 72 hours after the start of infusion
Dose normalised C_{\max}^a	Maximum observed plasma (peak) drug concentration divided by the dose administered

^a Calculated for total AZD4320 only

The following diagnostic parameters for plasma PK analysis will be provided:

λz lower	Lower (earlier) t used for λz determination
λz upper	Upper (later) t used for λz determination
λzN	Number of data points used for λz determination
Rsq	Statistical measure of fit for the regression used for λz determination
Rsq adj	Statistical measure of fit for the regression used for λz determination adjusted for the number of used data points (n obs)

Urine

Urine PK parameters will be calculated for total AZD4320 including renal clearance and amount excreted unchanged. Plasma and urine data:

Ae_{0-72}	Cumulative amount of unchanged drug excreted into urine from time 0 to 72 hours after the start of infusion
Fe	Percentage of dose excreted unchanged in urine

Ae ₀₋₇₂	Cumulative amount of unchanged drug excreted into urine from time 0 to 72 hours after the start of infusion
CLR	Renal clearance of drug from plasma

Additional PK parameters may be calculated as appropriate.

PK summary statistics

Plasma concentrations of AZD4320 will be summarised by nominal sample time. Plasma concentrations and derived PK parameters will be summarised by dose level and cohort. Plasma concentrations at each timepoint will be summarised according to dose and cohort by the following summary statistics:

- The geometric mean (g_{mean} , calculated as $\exp[\mu]$, where μ is the mean of the data on a logarithmic scale)
- Coefficient of variation (CV, calculated as $100 \sqrt{[\exp(s^2)-1]}$, where s is the standard deviation of the data on a log scale)
- $G_{\text{mean}} \pm$ standard deviation (calculated as $\exp[\mu \pm s]$)
- Arithmetic mean calculated using untransformed data
- Standard Deviation calculated using untransformed data
- Minimum
- Maximum
- Number of observations

The following summary statistics will be presented for the estimated PK parameters, as appropriate:

- G_{mean} , calculated as $\exp[\mu]$, where μ is the mean of the data on a logarithmic scale)
- CV, calculated as $100 \sqrt{[\exp(s^2)-1]}$, where s is the standard deviation of the data on a log scale)
- Arithmetic mean calculated using untransformed data
- Standard deviation calculated using untransformed data
- Minimum
- Maximum
- Number of observations

The pharmacokinetic data for AZD4320 will also be displayed graphically. Displays will include AZD4320 (total and released) plasma concentration subject profiles (on the linear and log scale) versus time and G_{mean} concentration (\pm standard deviation) versus time, stratified by

dose.

Scatter plots of PK parameters versus dose, or log-dose, may also be considered to assess dose proportionality.

CCI

CCI

CCI

11.7.9 Interim Analyses

Each cohort in Part B will have an internal IA for futility, with the potential to stop or trigger a combination expansion (to be added via a protocol amendment), followed by a sponsor decision towards further development if the cohort proceeds to full recruitment. During the IA, enrolment may be paused in order to fully evaluate the results. Data for the IA will include all data collected up to the point when the twelfth patient within the cohort has had the opportunity to complete one cycle of treatment with AZD0466 and is response evaluable as per [Table 21](#). The Evaluable for Response population will be used for this analysis. Contingent on the outcome of the IA, recruitment will then continue to full recruitment.

The interim analyses for efficacy will consist of summaries rates of best response (CR+CR_i) with one-sided lower 80% and upper 90% exact confidence limits compared to the cohort-specific target response rates as described in Section 11.7.2.

An IA for safety in Part B will take place at the same time as the analysis for efficacy, based on the Safety population. Rates of AEs leading to study treatment discontinuation will be compared to pre-specified criteria to inform a ‘stop’ or ‘consider’ decision. The unacceptable rate of AEs leading to study treatment discontinuation is set at 30%. For example, in 12 patients, one or fewer of these AEs would provide at least an 80% chance that the true rate is not greater than 30%. If 4 or more events are observed in 12 patients at the interim then there will be a lower than 10% chance that the rate is under 15% and the study may be stopped due to safety. If the IA takes place with a number other than 12 patients then the threshold rates of AEs leading to discontinuation may differ from the example provided.

The SAP will describe the planned interim analyses in greater detail.

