4.5 Criteria for Stopping or Pausing Study Recruitment

AstraZeneca reserves the right to pause recruitment, temporarily suspend, or permanently terminate this study or components of the study at any time. AstraZeneca may at any point during the study pause enrolment if at least one of the following occurs:

- Fatal event deemed related to study intervention by the Sponsor and in discussion with the SRC after full aetiological work-up. This will also result in a comprehensive review of safety.
- Unexpected and life-threatening events deemed related to study treatment by the Sponsor and in discussion with the SRC.
- Sponsor decision that study patients are placed at undue safety risk (also see Section 4.4).
- Sponsor decision to discontinue the development of the study treatment in the proposed indications.

During Part A of Module 1 and during Module 2, AstraZeneca pharmacovigilance process and the SRC will evaluate toxicities study-wide (including evaluation of previous doses).

During Part B of Module 1, AZD0466 monotherapy dose expansion, a safety analysis will be performed at the time of the first interim analysis (IA) in each cohort. The study recruitment may be paused, pending investigation by the Sponsor and in discussion with SRC, if > 30% of patients experience AEs leading to study treatment discontinuation (see Section 11.7.9), the SRC may decide to stop the study, modify the study, or continue the study, based on the overall risk benefit of the agent. In addition, individual cohort level stopping criteria are provided in Section 11.7.2.2. Throughout the expansions, the AstraZeneca safety team and the SRC, will regularly review cumulative safety data including, but not limited to, toxicities that meet the DLT criteria.

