11.4.1 Study Treatment – AZD0466

The study treatment investigational AZD0466 is described in **Table 15**.

Table 15 Study Treatment for Module 1

Study Treatment	AZD0466
Dosage Form	‘AZD0466 powder for concentrate for solution for infusion’ supplied with ‘Solvent for AZD0466 powder for concentrate for solution for infusion’.
Unit Dose Strength(s)	‘AZD0466 powder for concentrate for solution for infusion’: 500 mg per vial ^a ‘Solvent for AZD0466 powder for concentrate for solution for infusion’: 20 mL per vial ^a
Dose Level	As per dose escalation schema (Section 11.1.3.1)
Route of Administration	Intravenous
Handling Instructions	Refer to Handling Instructions
Provider	AstraZeneca R&D
Packaging and Labelling	AZD0466 powder for concentrate for solution for infusion will be provided in 500 mg vials. Each vial will be labelled as per country requirement. Solvent for AZD0466 powder for concentrate for solution for infusion will be provided in 20 mL vials. Each vial will be labelled as per country requirement.

^a AZD0466 powder for concentrate for solution for infusion 500 mg/vial is intended to be reconstituted with 20 mL custom solvent to produce AZD0466 concentrate for solution for infusion, 25 mg/mL. If required, AZD0466 concentrate for solution for infusion may be further diluted with custom solvent to produce AZD0466 solution for infusion for clinical dosing. Multiple vials of drug product and custom solvent may be used to achieve the required doses.

The dosing and dose escalation scheme are described in Section 11.1.3.1 and the SoA of this module (Section 11.5.1).

Treatment with AZD0466 will commence with a one-week ramp-up followed by weekly administration at the target dose. During ramp-up and while patients are considered at risk of TLS, patients must commence oral allopurinol and encouraged to drink 1.5 to 2 L of fluids at least 24 hours prior to AZD0466 infusion (Appendix F). Intravenous hydration is given on admission as outlined in Appendix F.

This intra-patient dose ramp-up comprises a starting dose on Day 1, subsequent titration to the intermediate dose on Day 4, and to the target dose on Day 8, with weekly IV administration thereafter at the target dose.

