11.7.2.2 Part B Monotherapy Dose Expansion

Separate expansion cohorts will enrol 4 distinct populations of patients with advanced haematological malignancies. Three of these expansion cohorts (Expansion Cohorts B1, B2, and B4) will recruit at least 21 patients, and one (Expansion Cohort B3) will recruit at least 25 patients. The total number of patients treated in Part B will be at least 88. These sample sizes have been determined to ensure confidence intervals constructed around the complete response rate (CR+CR_i), as calculated after all patients have had the opportunity to complete one treatment cycle, will provide sufficient information to enable decisions to be made around the likely success of future studies in these patient populations, using methodology described in [Frewer et al 2016](#).

Thresholds for decision making were set for each expansion cohort based on range of literature and expert opinion. For Expansion Cohort B1, a target value for response was set at 35%, with a lower reference value of 20%. If 7 or more responders are observed from 21 patients, there will be at least an 80% chance that the true response rate is at least 20%, which may promote a positive decision. If 4 or fewer responders are observed, then there is a 10% or less chance that the true rate is at least 35%, which may lead to a futility decision. If

the true rate of response is 15%, then, with 21 patients, there is an 80.3% probability of a result that may trigger a decision to stop further development in this population due to futility. This analysis will be performed using the ITT population.

An IA as described in Section 11.7.9 will be performed in each expansion cohort when 12 patients have had the opportunity for one cycle of treatment and is response evaluable as per [Table 21](#). The number of patients is based on the operating characteristics of the cohort-specific decisions using the approach as described in [Frewer et al 2016](#).

In Expansion Cohort B1, if 5 or more responders are observed from 12 patients, then there is at least an 80% chance that the true response rate is at least 20%, which may promote a decision to continue to full recruitment. It may be considered futile to continue development of this cohort if there is < 10% probability for the response rate to be greater than 35%. This translates to observing one or zero responders out of 12 patients.

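### Part B's only numeric safety look waits for the 12th response-evaluable patient, so patients who stop before the third target dose, for toxicity or any other reason, push it back

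*Protocol*

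**What the plan says.** Protocol 11.7.9 sets a numeric rule for adverse events leading to discontinuation of study treatment. The unacceptable rate is 30%. In an example of 12 patients, one or fewer events is favourable and four or more may lead to stopping, the latter judged against a rate of 15%. On timing it says: "An IA for safety in Part B will take place at the same time as the analysis for efficacy, based on the Safety population".

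The efficacy interim is triggered "when the twelfth patient within the cohort has had the opportunity to complete one cycle of treatment with AZD0466 and is response evaluable". Section 11.7.2.2 has the same trigger: "12 patients have had the opportunity for one cycle of treatment and is response evaluable". Table 21 in 11.7.3 defines the Evaluable for Response set as "All patients who have received at least 3 doses of AZD0466 at the target dose level in Cycle 1", and the Safety set as "All patients who received at least one dose of AZD0466". Under 11.4.1 patients go "to the target dose on Day 8, with weekly IV administration thereafter at the target dose", so target doses fall on Days 8, 15, 22 and 29 of a 35-day Cycle 1.

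Section 4.5 has a related criterion, a possible pause if more than 30% of patients have such events, and places it at the same moment: "a safety analysis will be performed at the time of the first interim analysis (IA) in each cohort". It also points to cohort-level stopping criteria in 11.7.2.2, but that section contains only response and futility rules. The second interim (11.7.5) follows full recruitment and has no stated numeric safety boundary. Section 11.7.10 says there is no data monitoring committee.

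**The concern.** The safety rule and its trigger count different patients. The rule counts everyone dosed. The trigger counts only those who reach a third target dose. A patient taken off treatment for an adverse event during ramp-up, or after one or two target doses, adds an event but brings the look no nearer. The Part A DLT-evaluable set uses the same three-dose requirement but also admits anyone who has had a DLT. The Part B trigger has no such provision.

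The look exists to catch a cohort with too many discontinuations before it is fully exposed. If many of those discontinuations come early, the number exposed before the look grows just when it should be kept small. The protocol sets no upper limit on the number dosed before the look, and gives no thresholds for a number other than 12.

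**Working it through.** **1. The plan's own boundaries (n = 12, exact binomial).**
- Favourable, 1 or fewer events: P(X ≤ 1 | 12, 0.30) = 0.085, so 91.5% confidence that the rate is not above 30%. Two events give P(X ≤ 2) = 0.253, or 74.7%, which misses the 80% level.
- Stop, 4 or more events: P(X ≥ 4 | 12, 0.15) = 0.092, below 10%. Three events give 0.264.

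Both printed boundaries reproduce.

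**2. Number dosed when the trigger is met.** Let f be the share of dosed patients who do not reach a third target dose, for any reason. The documents give no value for Part B, so the range below is an assumption. The number dosed when the 12th evaluable patient is reached is negative binomial with mean 12/(1−f). This is a lower bound on the number dosed at the look, because enrolment can continue while the 12th patient completes the 35-day cycle.

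| f | 12/(1−f) | P(fewer than 12 evaluable among 21 dosed) | Same, 25 dosed (B3) |
|---|---|---|---|
| 15% | 14.1 | under 0.1% | under 0.1% |
| 25% | 16.0 | 2.1% | 0.1% |
| 30% | 17.1 | 6.8% | 0.6% |
| 40% | 20.0 | 30.9% | 7.8% |

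The last two columns are P(Bin(n, 1−f) ≤ 11). They apply only if 21 (or 25) is the number recruited, as 11.7.2.2 suggests. Section 11.1.3.4 instead plans about 21 response-evaluable patients (25 in B3). On that reading the 12th evaluable patient always comes before the cohort is full, but more patients are dosed on the way.

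**3. Only early stops matter.** If half of the adverse-event discontinuations fall before the third target dose and nobody else drops out early, f is half the event rate. At event rates of 30%, 40% and 50% the mean is then 12/0.85 = 14.1, 12/0.80 = 15.0 and 12/0.75 = 16.0.

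**4. What the delay costs when the rule would have fired.** Take a true discontinuation rate of 30% and the simulated cohorts in which at least 4 of the first 12 dosed patients have discontinued. The look then comes on average about 7.0 further dosed patients later if all such stops are early, and about 2.9 later if half are.

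**5. Performance at the delayed look.** Apply the 15% reference rate and 10% level at the actual N. The smallest stopping count is 4 at N = 12, 5 at 13–17, 6 at 18–22 and 7 at 23–25. By simulation, with all stops early, the chance of meeting the stop criterion is about 55% at a true rate of 30% and 83% at 40%. With half early it is about 43% and 73%. At exactly 12 dosed it is 50.8% and 77.5%. The look is later but not materially weaker.

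**The case against.** The strongest reply is that the plan does not ignore these patients. The safety interim uses the Safety population, so every early stopper is counted once the look occurs. Section 11.7.9 offers 12 only as an example and says thresholds may differ at another number. Section 4.5 provides regular review of cumulative safety data by the sponsor's safety team and the SRC. It also lets enrolment be paused at any point for a related fatal event, related unexpected life-threatening events or undue risk. A joint look also suits a decision on overall benefit and risk. All of this stands. A reader might infer that early toxicity is left out of the analysis or goes unmonitored until the interim, and the documents support neither. What remains is that none of these safeguards carries a numeric boundary before the look.

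Three further inferences go too far.
- **The delay is proportional to toxicity.** It is not. Discontinuations after the third target dose do not delay the look, and early progression or death delays it just as early toxicity does.
- **The 25% fallout behind Part A's 36 evaluable of 48 enrolled is an early toxicity rate.** The amendment summary attributes it to disease progression, and a Part A patient with a DLT counts as evaluable.
- **The look could be missed altogether.** The 31% at f = 40% requires 21 to be a cap on patients dosed. Section 11.7.2.2 says at least 21, 11.1.3.4 counts response-evaluable patients, and the synopsis gives 88 across Part B as an upper limit. These statements differ, so the figure holds on one reading only.

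Finally, 11.7.9 leaves interim detail to the SAP. SAP version 2.0 removed its Part B content, so any fuller rule in version 1.0 cannot be checked here.

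**Conclusion.** The point holds as a defect in timing. Part B's only numeric safety criterion is tied to a count that patients stopping before about Day 22 never enter, so the look moves later as early dropout rises. The mean number dosed is at least 14 to 20 rather than 12 for an assumed early-stop share of 15% to 40%. On the recruited-patients reading of 21, the chance that a cohort fills before the trigger is met is 2%, 7% and 31% at f = 25%, 30% and 40%. On the response-evaluable reading it is zero.

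The result rests on f, which is assumed, and on reading the trigger as 12 evaluable patients. The wording in 11.7.9 is loose, but 11.7.2.2 and the use of the Evaluable for Response set with thresholds out of 12 support that reading. Delay is measured in patients dosed; a calendar delay would need an accrual rate, which is not given. SAP section 1 records that Part B was not initiated, so the point concerns the design and any reuse of it, not reported data.

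**What to change.** In Protocol 4.5 and 11.7.9, give the safety look its own trigger: the time when the 12th dosed patient in the cohort (Safety population) has had the opportunity to complete Cycle 1 or has discontinued. Leave the futility look on the response-evaluable trigger.

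Keep the stated criteria (reference rates 30% and 15%, levels 80% and 10%) and say how they apply. One option is to apply them to the first 12 patients dosed, where the printed boundaries hold as they stand. The other is to apply them to everyone dosed by then, with thresholds recalculated at the actual N. This choice has to be written down, because patients enrolled while the 12th completes Cycle 1 are already in the Safety population and N will exceed 12 unless enrolment is held.

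The cost is protocol wording and one additional discontinuation tabulation per cohort, with no extra patients or visits.
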